In addition, this proposal stems from a hospital-wide effort at Women & Infants Hospital (WIH) to reduce racial disparities among women of color in terms of frequency of severe maternal morbidity (SMM). SMM is a metric created by the Centers for Disease Control and Prevention that includes blood transfusion as well as adverse outcomes ranging from arrhythmia to eclampsia to intubation. SMM associated with hypertension is driven by asymptomatic postpartum hypertension. This is easily identified and managed prior to becoming SMM when patients adhere to recommended blood pressure checks after discharge. Excluding blood transfusion (which does not pertain to hypertension), the overall rate of SMM among women with hypertension during pregnancy who deliver at WIH is 6.6%. However, there is a significant difference along racial and ethnic lines: the rate of SMM in the setting of hypertension among black women is 6.8% compared to 4.5% among white women, and the rate of SMM in the setting of preeclampsia is 9.4% among Hispanic women compared to 4.9% among non-Hispanic women. The overall dual aim of the initiative is to reduce the disparity in rates of SMM among those with hypertension between black and white women and between Hispanic and non-Hispanic women by at least 33% by December 31, 2022. As part of WIH's equity initiative, automatic blood pressure cuffs (non Bluetooth enabled) will be provided to all women with hypertension at discharge from delivery hospitalization as part of

routine care. We plan to compare rates of SMM before versus after the hospital-wide implementation of SMS-based remote blood pressure monitoring. Thus, for this proposal, we will build the foundation for our long-term goal and for hospital-wide equity projects by exploring whether app-based remote blood pressure monitoring is required to decrease maternal morbidity compared to standard care with remote SMS blood pressure monitoring.

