For this pilot study, sample size limitations will require the use of surrogate markers of maternal morbidity to serve as patient outcomes, which have been selected based on evidence-based best-practices.¹⁻¹⁴ The primary clinical outcome for this study will be blood pressure measurement obtained three to ten days postpartum. Prespecified secondary outcomes include *postpartum readmission for blood pressure management* (e.g. rehospitalizations within 30 days of discharge), *adherence to evidence-based best-practices* (e.g. medications, antepartum surveillance, blood pressure ascertainment, postpartum blood pressure goal of <140/90), *composite severe maternal morbidity* (i.e. stroke, seizure/eclampsia, posterior reversible encephalopathy syndrome, pulmonary edema, heart failure, myocardial infarction, acute fatty liver of pregnancy, hemolysis, elevated liver enzymes and low platelets, placental abruption, post-partum hemorrhage, blood transfusion, acute kidney injury, and transaminitis), *postpartum maternal mortality*, and *composite neonatal morbidity* (i.e. umbilical artery pH <7.10, umbilical artery lactate, seizures, therapeutic hypothermia, hypoxic-ischemic encephalopathy, mechanical ventilation, intrauterine fetal death, neonatal death). We will also explore patient preferences as to treatment group via the Agency for Healthcare Research and Quality Consumer Assessment of Healthcare Providers and Systems (AHRQ CAHPS) survey and compared between both intervention groups and standard prenatal care.²⁵ CAHPS survey will provide mixed quantitative and qualitative assessments. Our *central hypothesis* is that app-based Bluetooth enabled blood pressure monitoring will improve adherence to evidence-based best practices and will demonstrate signals towards improved health equity and maternal morbidity outcomes compared to SMS-based remote blood pressure monitoring.

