2. STUDY DESIGN, METHODS, AND PROCEDURES

Study Design

2.1 Study Design: We will conduct a *pilot randomized control trial* of **120** women who deliver at Women and Infant's Hospital of Rhode Island (WIHRI) and plan to receive postpartum care at a WIHRI-affiliated clinic. We will use broad inclusion criteria and analyze data using the intention-to-treat principle to increase generalizability of the findings.

2.2 Eligibility criteria: Inclusion criteria: a) English- or Spanish-speaking b) maternal age ≥ 18 years old, c) smartphone ownership for remote blood pressure ascertainment, d) diagnosis of gestational hypertension, preeclampsia, or chronic hypertension, e) plan to receive postpartum care at a Women & Infants Hospital (WIH)-affiliated clinic. Exclusion criteria: a) fetal anomaly, b) prisoners, c) lack of smartphone, and d) inability to consent.

2.3 Screening, consent, and recruitment: Eligible women will be recruited at the Women and Infant's Hospital of Rhode Island (WIHRI) 's obstetrics units (obstetric triage, labor & delivery, antepartum care unit, and postpartum care unit) during their delivery hospitalization. Recruitment will be conducted by a research assistant or study principal investigator or co-investigator.

2.4 Randomization and blinding: Regardless of when their diagnosis of chronic hypertension, gestational hypertension, or preeclampsia with or without features occurs before or during delivery hospitalization, upon hospital discharge all patients will receive an automatic blood pressure cuff from WIHRI if their insurance does not cover this (or if they do not have one already); for patients whose insurance does cover automatic blood pressure cuffs, the provider will provide them with a prescription for this device at time of diagnosis. This is part of WIHRI's equity initiative related to hypertension: as stated previously, WIHRI has committed to provide non-Bluetooth enabled blood pressure cuffs to all eligible patients.

Those who consent to participate in the study, complete baseline study surveys, and receive a blood pressure cuff prior to discharge will be randomized 1:1 via a computer-generated randomization sequence to one of two protocols: *app based remote blood pressure monitoring* (intervention group) or and standard PNC with SMS-based monitoring (comparison group). The study staff will remain blinded to intervention, except for the research assistant who will be, by necessity, unblinded.

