They will receive the following per their randomization group:

Standard care (comparison group)

All women will receive education and counseling from their physician providers on evidence-based best-practices and red-flags for pregnancy's complicated by chronic hypertension, preeclampsia, or gestational hypertension. They will participate in WIHRI's ongoing equity initiative using automatic blood pressure cuffs in a remote hypertension monitoring program supported by a nurse practitioner and community health worker.

App-based remote blood pressure monitoring (intervention group)

Women in this group will receive a Bluetooth-enabled automatic blood pressure cuff that sends messages through an affiliated smartphone application to providers upon recording each measurement. This affiliated smartphone application will also contain education on hypertension management. Upon receipt of the blood pressure cuff, participants will be instructed to set up the program/app such that the research assistant (RA) will receive all recorded blood pressure managements. All patients will receive instructions on how to obtain blood pressure and will be instructed to call their on-call provider if the blood pressure is $>160/110$ mmHg. The RA will review each patient's blood pressure log daily to ensure blood pressures remain mild-range (i.e. 140-159/90-109 mmHg) or less.

2.5 Study procedures: Perinatal data will be collected and directly entered by the research assistant or principal investigators into REDCap, a secure database hosted by WIHRI. Data will be collected on a rolling basis to ensure timely collection and monitoring for unseen adverse events.

Potential challenges and alternative approaches: Obtaining our target sample size may be challenging due to the incidence of hypertension diseases of pregnancy in the literature. However, we anticipate having a sufficient population from which to recruit for this pilot study given the 18 month study period and the relatively small sample study. However, should our target sample size be lower than expected, we may expand recruitment into private practice groups who have separate admitting privileges.

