We will also explore patient preferences as to treatment group via the Agency for Healthcare Research and Quality Consumer Assessment of Healthcare Providers and Systems (AHRQ CAHPS) survey and compared between both intervention groups and standard prenatal care.²⁵ Per AHRQ guidelines, 100 CAHPS surveys must be completed in a pilot study to determine a difference in patient experience between care models.²⁵ Our study population of **60 women** per group (120 women total) is anticipated to generate ~100 completed surveys per group (200 total), based on an anticipated response rate of 80% and each participant completing two surveys. Upon enrollment, participants will choose whether they desire to complete the AHRQ CAHPS surveys in paper, online through email, or via a text-message platform; regardless of route, surveys will be collected at randomization and at ~30-45 days postpartum.

On the second survey, participants will also complete a validated scale, the Decision Regret Scale.²⁶ Of note, both the AHRQ CAHPS study and the Decision Regret Study are already validated in Spanish.

2.6 Data Management, Sources of Materials, Records/Data to be reviewed: Antepartum, maternal/neonatal, pregnancy, and perinatal data will be collected and directly entered by the research assistant or principal investigator into REDCap, a secure database hosted by WIHRI. All primary and secondary outcomes will be entered into REDCap by the RA or study team. Thus, the data to be reviewed will only be collected by key study personnel. In addition, pregnancy characteristics (maternal weight, disease comorbidities, etc.) and demographic information (reported race/ethnicity, insurance type, zip code) will be collected post-delivery and entered into REDCap. Prior to data analysis, all patient identifiable information will be stripped to ensure patient confidentiality. Our REDCap database will be encrypted by multiple levels of password protection (accessing computer, network, and logging into database) that will only be accessible by key research personnel. Anti-virus software is installed and up to date and the operating system is up to date with all Windows and Apple updates.

Material/Specimen Management: No specimens will be stored outside of standard care (such as umbilical cord gases processed by laboratory per usual clinical protocol).

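### The plan does not say which records show that the 3-10 day blood pressure check was done, and it lets the one unblinded staff member enter that primary outcome

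*Combined protocol and SAP*

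**What the plan says.** **Outcome.** Section 1: "The primary clinical outcome for this study will be blood pressure measurement obtained three to ten days postpartum". Section 2.6 (Study outcomes and Power) instead makes the primary adherence to the recommended check in the same window, tied to standard of care, and sizes the trial on adherence of 50% versus 80%. Neither statement names a qualifying record, such as a clinic or chart entry, app log, SMS programme log or patient report.

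**Route of readings, app arm.** Section 2.4 has the cuff send each reading through the app to providers. For the RA, "participants will be instructed to set up the program/app such that the research assistant (RA) will receive all recorded blood pressure managements". Under the same heading, the RA reviews each patient's "blood pressure log daily to ensure blood pressures remain mild-range" or lower.

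**Route of readings, comparison arm.** Participants join a "remote hypertension monitoring program supported by a nurse practitioner and community health worker". No route from that programme to REDCap is described.

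**Entry and blinding.** Section 2.4: "The study staff will remain blinded to intervention, except for the research assistant who will be, by necessity, unblinded". Section 2.5 has perinatal data "directly entered by the research assistant or principal investigators into REDCap". The section on data management, also numbered 2.6, says: "All primary and secondary outcomes will be entered into REDCap by the RA or study team". No blinded determination of the primary outcome is described.

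**The concern.** The intervention is itself a recording device. If the sources that prove a check are not fixed in advance and searched alike in both arms, a check that was better recorded cannot be told from a check that was more often done. Two groups that check equally often could then appear to differ, or a real difference could be hidden.

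The second weakness is who decides. The plan has blinded study staff who are allowed to enter outcomes, yet it equally allows entry by the one person who knows the arm and who may also be receiving the app readings. That gives up a safeguard already available.

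The trial is a pilot, but its primary outcome has an alpha and a target difference, and the data are meant to support a later efficacy trial. An artefact of recording would carry into that decision.

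**Working it through.** **Inputs from the plan.** 60 per group, 1:1 allocation, two-sided alpha 0.05, adherence 50% versus 80%, chi-square or Fisher's exact test (Sections 2.4, 2.6 and 2.7). Power is not stated.

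**The plan's own figure.** Relative increase: 0.50 × 1.6 = 0.80, as stated. Power at 60 per arm by the pooled normal formula:
- mean proportion 0.65; standard error under the null √(2 × 0.65 × 0.35 / 60) = 0.0871
- standard error under the alternative √((0.50 × 0.50 + 0.80 × 0.20) / 60) = 0.0827
- (0.30 − 1.96 × 0.0871) / 0.0827 ≈ 1.56, so power is about 94%

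Exact enumeration gives 94.2% (chi-square without continuity correction) and 91.3% (Fisher). So 120 is enough for the stated effect, and the sample size is not in dispute. The number 120 itself cannot be derived without a stated power.

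**Effect of unequal capture.** The documents give no capture rate for either arm, so the loss rates below are assumptions. Let t be true adherence in both arms (no true difference) and L the share of completed checks that go unrecorded in one arm, with none lost in the other. Recorded adherence is then t in one arm and t × (1 − L) in the other, and the false gap is t × L. The rejection probability is the sum, over all pairs of binomial counts with n = 60 per arm, of the probability of each pair for which the test gives p ≤ 0.05.

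False-positive rate, chi-square / Fisher:

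| L | t = 50% | t = 65% | t = 80% |
|---|---|---|---|
| 0 | 5.5% / 3.5% | 5.0% / 3.1% | 5.0% / 2.8% |
| 5% | 6.4% / 4.2% | 6.6% / 4.2% | 8.4% / 5.2% |
| 10% | 9.1% / 6.3% | 11.4% / 7.9% | 18.0% / 12.4% |
| 20% | 20.5% / 15.6% | 31.0% / 24.6% | 51.0% / 42.0% |
| 30% | 39.2% / 32.2% | 59.1% / 51.7% | 82.1% / 75.8% |

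At L = 10% the false gap is 0.50 × 0.10 = 5 points at 50% adherence and 0.80 × 0.10 = 8 points at 80%. True adherence is varied because the plan gives 50% only as a baseline rate, while Section 2.8 says text-message monitoring improves adherence; both arms are monitored remotely.

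**Direction.** The rates are the same whichever arm has the loss; only the favoured arm changes. At t = 50% and L = 10%, 8.5 of the 9.1 points (chi-square) favour the arm without loss.

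**The opposite case.** If the plan's 80% versus 50% is true and 10% of app-arm checks are unrecorded, perhaps through failed set-up, recorded app adherence is 0.80 × 0.90 = 72%. Power falls from 94% to 70% (chi-square) or from 91% to 63% (Fisher).

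Equal proportional loss in two arms with equal adherence creates no false gap.

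**The case against.** The best defence is that ascertainment may in practice be common to both arms. Every participant must plan postpartum care at a hospital-affiliated clinic (Section 2.2), the same personnel collect data for both arms into one database, and the outcome is tied to a standard-of-care check. A shared chart source is a plausible reading. It is nowhere stated, though, and Section 2.5 allows recruitment to expand into private practices. The daily log review may also cover both arms, since the text speaks of each patient, but it stands under the app heading and serves surveillance of blood pressure range; it does not define the outcome.

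Three stronger readings are tempting and are not supported.
- *The app arm will look better because the RA receives its readings automatically.* Automatic messages go to providers. Receipt by the RA depends on participants setting the app up, and the comparison programme has its own staff. Neither unequal capture nor its direction is shown.
- *Only checks after discharge count.* Section 1 does say morbidity is averted "when patients adhere to recommended blood pressure checks after discharge", but that is background. Neither outcome statement contains the restriction.
- *Any gap from transmission is an artefact.* If a check means a reading that reaches the care team, an unsent reading is non-adherence, and easier transmission is part of what the app offers. The documents do not settle which meaning applies, which is itself a reason to define the outcome.

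It is also fair that a dated yes/no event leaves little room for assessor judgement. The event may be objective, but its count still depends on which records are searched.

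**Conclusion.** The point stands as a gap in definition and a missed safeguard, not as a demonstrated bias. It is certain that the two primary-outcome statements differ, that neither names the qualifying records, that the comparison arm has no stated path to the database, and that the unblinded RA may enter the result. The size and direction of any bias are unknown.

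If 10% of checks went unrecorded in one arm only, the false-positive rate would be 9% or 6% (chi-square or Fisher) at 50% adherence and 18% or 12% at 80%. These figures assume 60 analysed per arm, no true difference and no loss in the other arm. The larger values in the table need loss rates for which the documents give no basis and should not be read as forecasts. The change should be made because it is cheap and uses staff the plan already has.

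**What to change.** 1. Reconcile Section 1 and Section 2.6 (Study outcomes and Power) into one primary outcome: yes/no, a blood pressure check done on postpartum days 3-10. The yes/no form fits the adherence proportions used for the sample size.
2. Search the same dated sources for every participant in both arms: clinic and chart records plus the participant's app log or SMS programme log. Report a chart-only version as a sensitivity analysis.
3. In the data management section, have blinded study-team members, who may already enter data, determine the primary outcome from the dated records with arm masked where possible, instead of the RA.
4. Make the change by amendment before any comparison by arm. Recruitment has already begun, so a rule chosen after such a comparison could be driven by the data.

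**Cost.** An amendment, retrieval of records including those of participants already enrolled, and some investigator time. Masking will be imperfect where a record reveals the arm. Readings taken at home but never sent in will remain uncounted, so the chart-only analysis is needed alongside. Sample size, treatment and visits do not change.

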2.8 Plan to include a diverse population

Table 2. Composite maternal and neonatal morbidity outcomes

Composite maternal morbidity	
Stroke	
Seizure/eclampsia	
Acute fatty liver of pregnancy	
Posterior reversible encephalopathy syndrome	
Pulmonary edema	
Heart failure	
Hemolysis elevated liver enzymes and low platelets	
Placental abruption	
Post-partum hemorrhage	
Acute kidney injury	
Transaminitis	
Composite neonatal morbidity	
Umbilical artery pH < 7.10	
Umbilical artery lactate	
Seizures	
Therapeutic hypothermia	
Hypoxic-ischemic encephalopathy	
Mechanical ventilation (i.e. intubation)	
Supplemental oxygen 0-6 hours, 6-12 hours, 12-24 hours, >24 hours of life	
Intrauterine fetal death	
Neonatal death	

Inclusion of minorities: This proposal aims to reduce health inequity among women of color with gestational hypertension, preeclampsia, or chronic hypertension. Rates of hypertensive disease in pregnancy are higher among minority women. Given this is our target population, we anticipate that a significant proportion of women included in our study will be minorities. Recruitment will be conducted at prenatal clinics by a research assistant or member of the study team.

Inclusion of fetuses, neonates, and pregnant women: Recent data suggests utilizing remote blood pressure monitoring via text messaging and automatic blood pressure cuffs improves adherence to recommended care.¹⁵⁻¹⁷ As this practice should become standard of care, WIHRI plans to implement SMS-based remote blood pressure monitoring hospital wide for all eligible patients. However, the effect of SMS-based messaging on reducing maternal morbidity outcomes pertaining to hypertension is unknown. In this pilot study, we will compare standard of care (SMS-based remote blood pressure monitoring) to a high quality digital health intervention (smartphone app provided patient education and linked Bluetooth-enabled blood pressure monitoring). This innovative study will allow us to obtain pilot data to determine whether additional digital health support (Bluetooth enabled cuff and app-provided education) is more effective at improve health equity among women of color who deliver at WIH when compared to standard care (SMS-based remote blood pressure monitoring).

3.9 Participant Reimbursement: No reimbursement will be provided for participation, but all participants who complete all required surveys will be entered into a raffle with a prize of \$100

